4.1.1 Study flow

The study is comprised of the following periods:

[figure not shown]
- Screening
- Treatment

- End of Treatment (EOT)
- Safety follow-up: patients will be followed for safety at 30-Days, 60-Days, 90-Days, 120-Days, and 150-Days after the last dose of PDR001 ([Section 7.1.7](#))
- Post-treatment efficacy follow-up:
 - Before the primary analysis cut-off date (10-Aug-2018), patients who discontinue treatment for reasons other than irRECIST PD will have tumor assessments per [Table 7-1](#) until withdrawal of consent, death, lost to follow-up, or eventual irRECIST PD per BIRC even if new antineoplastic treatment (ANP) is started ([Sections 7.1.8](#) and [Section 7.2.1](#))
 - After the primary analysis cut-off date (10-Aug-2018), post-treatment efficacy follow-up will be discontinued. Therefore, any patients, who are in post-treatment efficacy follow-up at the time of the primary analysis cut-off date, will enter the survival follow-up after completion of the safety follow-up. If clinically indicated, patients may continue to undergo tumor response assessments during the safety follow-up according to local or institutional standard of care; however these tumor response assessments will no longer be reported in the eCRF.
- Survival follow-up: patients will be followed for survival every 3 months after the completion of safety or efficacy follow-up, whichever is last

For a diagram of the study flow, see Figure 4-2. Patients will undergo safety and efficacy assessments during screening, treatment, and follow-up as outlined in [Table 7-1](#) visit evaluation schedule.

This study will use third-party vendors for central imaging, central laboratory, ePRO (e.g., electronic tablet devices to collect patient-reported outcomes (PRO) data), and eligibility checklist plus drug supply management via Interactive Response Technology (IRT). After the primary analysis cut-off date (10-Aug-2018) ePRO and central tumor response assessments will no longer be performed and/or collected.

Figure 4-2 Study flow

*After the the primary analysis cut-off date (10-Aug-2018), post-treatment efficacy follow-up will no longer be performed.

4.2 Timing of interim analysis and design adaptations

A planned interim analysis (IA) will be conducted after approximately 30 patients in the well-differentiated NET group have undergone the first 3 radiological assessments (expected around week 24) or have shown disease progression or have discontinued efficacy follow-up for any other reason. All available efficacy and safety data from well-differentiated NET and poorly differentiated GEP-NEC groups up to the cut-off date will be used for the IA and reviewed by the Steering Committee (see [Section 10.7](#) for more details). It is expected that at the time of the interim analysis all patients from the poorly-differentiated GEP-NEC group have undergone at least 2 radiological assessments. The study will not be stopped at the interim analysis for efficacy reasons regardless of results and will be continued until mature data from all patients become available.

4.3 Definition of end of study

Cut-off date for the primary analysis will be 1 year after Last Patient First Treatment (LPFT) in the initially enrolled well-differentiated NET group. This analysis will include data from patients with well-differentiated NET and poorly-differentiated GEP-NEC groups who were enrolled in the study. It is expected that at the time of this analysis all patients from the original poorly-differentiated GEP-NEC group will have at least 11 months follow-up. This analysis will be summarized in the clinical study report (CSR).

If the analysis results are not conclusive or do not meet the pre-specified study criteria (refer to [Section 10.4](#)), the treatment continuation for patients who are benefitting from PDR001

treatment will be assessed on a case-by-case basis in consultation with the sponsor. Patients who discontinue study treatment will complete the safety follow-up period.

The end of study is defined as the earliest occurrence of one of the following :

- All patients have discontinued treatment and completed safety follow-up period.
- If another clinical study becomes available that can continue to provide treatment with PDR001 in this patient population and all ongoing patients are eligible to be transferred to that clinical study (and do not meet any discontinuation criteria from study CPDR001E2201).
- At the end of the study, every effort will be made to continue provision of investigational treatment outside this study through an alternative setting to patients who in the opinion of the Investigator are still deriving clinical benefit.

4.4 Early study termination

If the study is stopped for safety reasons, recruitment will be terminated, and the treatment continuation of patients who are deriving benefit from PDR001 treatment will be assessed on a case-by-case basis in consultation with the sponsor.

The study can be terminated at any time for any reason by Novartis. Should this be necessary, the patient should be seen as soon as possible and the same assessments should be performed as described in [Section 7.1.6](#) for a discontinued or withdrawn patient. The investigator may be informed of additional procedures to be followed in order to ensure that adequate consideration is given to the protection of the patient's interests. The investigator will be responsible for informing IRBs and/or ECs of the early termination of the trial.

5 Population

5.1 Patient population

The study will include two groups of adult patients with advanced (unresectable or metastatic):

- Well-differentiated (G1/2), non-functional, neuroendocrine tumor of GI, pancreatic or thoracic (lung/thymus) origin who have progressed on prior treatment
- Poorly-differentiated GEP-NEC who have progressed on or after one prior chemotherapy regimen.

Patients enrolled in this study are not permitted to participate in additional parallel investigational drug or device studies.

The investigator or designee must ensure that only patients who meet all the following inclusion and none of the exclusion criteria are met.

5.2 Inclusion criteria

Patients eligible for inclusion in this study have to meet **all** of the following criteria:

1. Written informed consent must be obtained prior to any screening procedures
2. Adult males or females \geq 18 years at screening.
3. Pathologically confirmed, advanced (unresectable or metastatic):

- Well-differentiated (G1 /2) based on local pathology report, non-functional neuroendocrine tumor of GI, pancreatic or thoracic (including lung and thymus) origin.
 - Poorly-differentiated GEP-NEC based on local pathology report
4. No active symptoms related to carcinoid syndrome during the last 3 months prior to start of study treatment.
5. Patients must have received prior treatment for advanced disease:
- Well-differentiated NET group:
 - a. Thoracic (lung and thymus origin) cohort:
 - Thymus origin: at least one prior systemic therapy according to investigator's choice
 - Lung origin: at least one prior systemic therapy is required, which must include everolimus.
 - b. GI cohort: at least two prior systemic regimens, which must include everolimus. Prior systemic therapies may include: somatostatin analogs, PRRT, and/or chemotherapy.
 - c. pNET cohort: at least two prior systemic regimens, which must include everolimus and/or sunitinib. Prior systemic therapies may include: somatostatin analogs, PRRT and/or chemotherapy.
- Note: For well-differentiated NET, prior treatment with interferon alpha is allowed provided that it is not the last treatment received prior to study entry.
- Poorly-differentiated GEP-NEC group: at least one prior chemotherapy regimen according to Investigator's choice.
6. Radiological documentation of disease progression :
- Well-differentiated NET group: Disease progression while on/or after the last treatment, and this progression must have been observed within 6 months prior to start of study treatment (i.e. maximum of 24 weeks from documentation of progression until study entry). Disease must show evidence of radiological disease progression based on scans performed not more than 12 months apart.
 - Poorly-differentiated GEP-NEC group: Disease progression while on or after prior treatment.
7. At least one measurable lesion assessed by CT and/or MRI according to RECIST 1.1.
Note: Any lesions which have been subjected to percutaneous therapies or radiotherapy should not be considered measurable, unless the lesion has clearly progressed since the procedure.
8. Patient must have an Eastern Cooperative Oncology Group (ECOG) performance status 0-2.
9. Tumor biopsy material must be provided for all patients [REDACTED]:
- Well-differentiated (G1/2) NET: Biopsy material must be provided following the diagnosis of metastatic disease. The tumor sample must be collected from a metastatic site not previously irradiated and **should preferably be taken within 6 months but not more than 24 months prior to start of study treatment.**
- [REDACTED]

- Poorly-differentiated GEP-NEC: Biopsy material must be collected from the primary tumor or from a metastatic site not previously irradiated, **taken not more than 24 months prior to start of study treatment.**
10. Women of childbearing potential must have had a negative serum pregnancy test within 72 hours prior to the start of study treatment. Highly effective contraception must be used while on study.
 11. Patient is deemed by the investigator to have the ability and means to be compliant with the protocol (treatment and follow-up).
 12. Patient must meet the following laboratory values at the screening visit:
 - Absolute Neutrophil Count $\geq 1.5 \times 10^9/L$
 - Platelets $\geq 75 \times 10^9/L$
 - Hemoglobin (Hgb) ≥ 9 g/dL
 - Serum creatinine < 1.5 mg/dL
 - Total bilirubin ≤ 1.5 x ULN
 - Aspartate transaminase (AST) ≤ 3.0 x ULN, except for patients with liver metastasis, if AST ≤ 5.0 x ULN
 - Alanine transaminase (ALT) ≤ 3.0 x ULN, except for patients with liver metastasis, if ALT ≤ 5.0 x ULN

5.3 Exclusion criteria

Patients eligible for inclusion in this study **must not meet any** of the following criteria:

1. Well-differentiated, grade 3 neuroendocrine tumors; poorly-differentiated neuroendocrine carcinoma of any origin (other than GEP-NEC); including NEC of unknown origin, adenocarcinoid, and goblet cell carcinoid.
2. Pretreatment with interferon as last treatment prior to start of study treatment
3. Prior treatment for study indication with:
 - a. Antibodies or immunotherapy within 6 weeks before the first dose of study treatment.
 - b. PRRT administered within 6 months of the first dose.
 - c. Systemic antineoplastic therapy (including cytotoxic chemotherapy, and toxin immune conjugates) or any experimental therapy within 14 days or 5 half-lives, whichever is longer, before the first dose of study treatment. For cytotoxic agents that have major delayed toxicities a washout period of more than 6 weeks is indicated (examples are nitrosoureas and mitomycin C).
 - d. Tyrosine kinase inhibitors within 14 days or 5 half-lives, whichever is longer, before the first dose of study treatment.
 - e. Prior PD-1- or PD-L1-directed therapy.
 - f. Cryoablation, radiofrequency ablation, or trans-arterial embolization of hepatic metastases within 2 months before the first dose of study treatment.
4. Systemic chronic steroid therapy (≥ 10 mg/day prednisone or equivalent) or any immunosuppressive therapy 7 days prior to planned date for first dose of study treatment. Topical, inhaled, nasal and ophthalmic steroids are allowed.

5. Any untreated central nervous system (CNS) lesion. However, patients are eligible if: a) all known CNS lesions have been treated with radiotherapy or surgery and b) patients remained without evidence of CNS disease progression ≥ 4 weeks after treatment and c) patients must have discontinued corticosteroid therapy for ≥ 2 weeks.
7. Malignant disease, other than that being treated in this study. Exceptions to this exclusion include the following: malignancies that were treated curatively and have not recurred within 2 years prior to study treatment; completely resected basal cell and squamous cell skin cancers and any completely resected carcinoma in situ.
8. Major surgery, open biopsy, or significant traumatic injury within 2 weeks prior to start of study treatment. Note: Minor procedures and percutaneous biopsies or placement of vascular access device require 7 days wash-out period prior to start of study treatment
9. Anticipation of the need for major surgical procedure during the course of the study
10. Radiation therapy within 4 weeks prior to start of study treatment (palliative radiotherapy to bone lesions allowed within 2 weeks prior to study treatment start)
12. History of severe hypersensitivity reactions to other monoclonal antibodies which in the opinion of the investigator may pose an increased risk of a serious infusion reaction.
13. Impaired cardiac function or clinically significant cardiac disease, including any of the following:
 - Clinically significant and/or uncontrolled heart disease such as congestive heart failure requiring treatment (New York Heart Association (NYHA) grade ≥ 2)
 - Uncontrolled hypertension with or without antihypertensive medication. Initiation or adjustment of antihypertensive medication is allowed prior to screening or clinically significant arrhythmia,
 - QTcF >480 ms on screening ECG or congenital long QT syndrome, acute myocardial infarction or unstable angina pectoris < 3 months prior to study entry.
14. Autoimmune disease that has required systemic treatment (i.e. disease modifying agents, steroids, or immunosuppressive drugs). Stable and adequate controlled endocrinopathies requiring replacement therapy (i.e. thyroid hormones, insulin, or physiologic corticosteroids) are not considered as systemic treatment and therefore are allowed.
15. Active infection requiring systemic antibiotic therapy.
16. Known history of testing positive for Human Immunodeficiency Virus (HIV) infection.
17. Patients with active Hepatitis B infection (HBsAg positive) will be excluded.
 - Note: Patients with prior Hepatitis B (anti-HBc positive, HBsAg and HBV-DNA negative) infection are eligible.
18. Patients with positive test for hepatitis C ribonucleic acid (HCV RNA).
 - Note: Patients in whom HCV infection resolved spontaneously (positive HCV antibodies without detectable HCV-RNA) or those that achieved a sustained virological response after antiviral treatment and show absence of detectable HCV RNA ≥ 6 months (with the use of IFN-free regimens) or ≥ 12 months (with the use of IFN-based regimens) after cessation of antiviral treatment are eligible.
19. Any medical condition that would, in the investigator's judgment, prevent the patient's participation in the clinical study due to safety concerns, compliance with clinical study procedures or interpretation of study results.

20. Use of any live vaccines against infectious diseases within 4 weeks of initiation of study treatment.
21. Presence of \geq CTCAE grade 2 toxicity (except alopecia, peripheral neuropathy, and ototoxicity, which are exclusion criteria if \geq CTCAE grade 3) due to prior cancer therapy.
22. Not able to understand and to comply with study instructions and requirements.
23. Pregnant or nursing (lactating) women confirmed by a positive hCG laboratory test within 72 hours prior to initiating study treatment. Note: Low levels of hCG may also be considered a tumor marker, therefore if low hCG levels are detected, another blood sample at least 4 days later must be taken to assess the kinetics of the increase and transvaginal ultrasound must be performed to rule out pregnancy.
24. Women of child-bearing potential, defined as all women physiologically capable of becoming pregnant, **unless** they are using highly effective methods of contraception during dosing and for 150 days after stopping treatment with PDR001. Highly effective contraception methods include:
 - a. Total abstinence (when this is in line with the preferred and usual lifestyle of the patient). Periodic abstinence (e.g., calendar, ovulation, symptothermal, post-ovulation methods) and withdrawal are not acceptable methods of contraception
 - b. Female sterilization (have had surgical bilateral oophorectomy with or without hysterectomy), total hysterectomy, or tubal ligation at least six weeks before taking study treatment. In case of oophorectomy alone, only when the reproductive status of the woman has been confirmed by follow up hormone level assessment
 - c. Male sterilization (at least 6 months prior to screening). The vasectomized male partner should be the sole partner for that patient
 - d. Use of oral, injected or implanted hormonal methods of contraception or placement of an intrauterine device (IUD) or intrauterine system (IUS), or other forms of hormonal contraception that have comparable efficacy (failure rate $<1\%$), for example hormone vaginal ring or transdermal hormone contraception

Note: In case of use of oral contraception women should have been stable on the same pill for a minimum of 3 months before taking study treatment.

Women are considered post-menopausal and not of child bearing potential if they have had 12 months of natural (spontaneous) amenorrhea with an appropriate clinical profile (i.e. age appropriate, history of vasomotor symptoms) or have had surgical bilateral oophorectomy (with or without hysterectomy), total hysterectomy, or tubal ligation at least six weeks prior to enrollment. In the case of oophorectomy alone, a woman is considered not of child bearing potential only when her reproductive status has been confirmed by follow up hormone level assessment.

26. Known history or current interstitial lung disease or non-infections pneumonitis.
27. Use of somatostatin analogs or any other medications administered to control active symptoms related to carcinoid syndrome during the last 3 months prior to start of study treatment.

6 Treatment

6.1 Study treatment

For this study, the investigational drug is PDR001. The study treatment is defined as PDR001. PDR001 is supplied as PDR001 100 mg powder for solution for infusion. PDR001 will be diluted in dextrose 5% in water (D5W). Due to incompatibility, 0.9% sodium chloride solution must not be used. PDR001 will be administered at a dose of 400 mg every 4 weeks given as a 30 minute infusion.

PDR001 infusion must take place in a facility with appropriate resuscitation equipment available at the bedside and a physician readily available during the period of drug administration.

All dosages prescribed and administered to patients and all dose interruptions and changes during the study must be recorded on the Dosage Administration Record (DAR) eCRF page.

6.1.1 Dosing regimen

Table 6-1 Dose and treatment schedule

Study treatments	Pharmaceutical form and route of administration	Strength	Frequency and/or Regimen	Dose Administered
PDR001	Powder for solution for infusion in vial for i.v. infusion	4 x 100 mg vials	Every 4 weeks	400 mg

PDR001 will be administered via intravenous infusion over 30 minutes (up to 2 hours, if clinically indicated) once every 4 weeks (+/- 7 days window). PDR001 will be administered on Day 1 of every cycle. Each cycle is 28 days. The actual date of Cycle Day 1 will be used to project the dates of future cycles. The dose may be interrupted for up to 12 weeks. The safety assessments (as per [Table 7-1](#) and [Section 7.2.2](#)) should be performed according to the actual day of infusion.

6.1.2 Ancillary treatments

Patients should not receive pre-medication to prevent infusion reaction before the first infusion of PDR001 as a way to determine if pre-medication is necessary. If a patient experiences an infusion reaction, he/she may receive pre-medication prior to subsequent dosing days. The pre-medication should be chosen per institutional standard of care at the discretion of the treating physician.

Acute allergic reactions should be treated as needed per institutional standard of care. In the event of anaphylactic/anaphylactoid reactions, this includes any therapy necessary to restore normal cardiopulmonary status. If a patient experiences a severe anaphylactic/anaphylactoid reaction, the infusion should be discontinued immediately. The patient may only resume study treatment following discussion with Novartis.

Patients should be treated in a facility equipped for cardiopulmonary resuscitation. Appropriate resuscitation equipment should be available at the bedside and a physician readily available.

Guidelines on management of PDR001 infusion reactions are provided in [Section 6.3.1.2](#).

The CTCAE category of “Infusion related reaction” should be used to describe PDR001 infusion reactions, unless the investigator considers another category, such as “Allergic reaction,” “Anaphylaxis,” or “Cytokine release syndrome” more appropriate in a specific situation.

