Based on literature from compounds with similar mechanism of action of PDR001, instructions have been developed regarding how to identify, assess severity and manage irAEs that may occur in patients receiving PDR001. The dose modification requirements and AE management guidelines for the potential irAEs are provided in the following tables: diarrhea/colitis ([Table 6-2](#)), hepatitis (liver laboratory alterations) ([Table 6-3](#)), skin (rash) ([Table 6-4](#)), nephritis ([Table 6-5](#)), pneumonitis ([Table 6-6](#)), encephalitis ([Table 6-7](#)), endocrinopathies ([Table 6-8](#)), PDR001-infusion reaction & cytokine release syndrome ([Table 6-9](#)), and other potential immune-related AEs of special interest ([Table 6-10](#)). Any grade 4 irAE must result in permanent discontinuation of PDR001.

Under the category of OTHERS ([Table 6-11](#) and [Table 6-12](#)) are included several irAE of interest that must be managed specifically and for which not specific guidance are provided in the table below. OTHERS include (but is not restricted to) the following events: autoimmune neuropathy, demyelinating polyneuropathy, Guillain-Barre, myasthenia Gravis-like syndrome, non-infectious myocarditis, non-infectious pericarditis, pancreatitis and rapid onset of grade 3 fatigue in the absence of disease progression.

Patients receiving PDR001 may experience irAEs other than those listed in this document; therefore, all AEs of unknown etiology associated with drug exposure should be evaluated to determine if they are possibly immune-related. In cases where the specific irAEs are not listed in the tables below, the investigator should follow the dose modification requirements in [Section 6.3.1.3](#) which details the measures to be taken for suspected (they could be potentially immune-related or non-immune-related) AEs. Investigators are encouraged to contact the sponsor as needed to discuss cases that warrant separate discussion outside of the scope of the current instructions.

The dosing modification requirements are mandatory; however, the AE management guidelines are recommendations and can be modified according to local practices. The management of irAEs may include initiation of antibiotics for prophylaxis against opportunistic infections.

Table 6-2 Mandatory dose modification requirements and recommended clinical management guidelines for potential immune-related diarrhea/colitis

Diarrhea/Colitis (NCI-CTCAE v4.03)		

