Symptomatic endocrinopathy (e.g., hypophysitis, adrenal insufficiency, hypothyroidism, hyperthyroidism)	
 Consider Endocrinology consultation Rule out infection and sepsis with appropriate cultures and imaging Treat with an initial dose of methylprednisolone 1 to 2 mg/kg intravenously followed by oral prednisone 1 to 2 mg/kg per day. Replacement of appropriate hormones may be required as the steroid dose is tapered Hypophysitis with clinically significant adrenal insufficiency and hypotension, dehydration, and electrolyte abnormalities (such as hyponatremia and hyperkalemia) constitutes adrenal crisis Consider hospitalization and intravenous methylprednisolone should be initiated. 	
1st occurrence:
 
 Interrupt PDR001 until symptomatic recovery to mild (e.g. grade 1) or no symptoms Once recovered, restart PDR001 treatment at the same dose and schedule 
AE resolution to mild or no symptoms must occur within a period of 12 weeks since symptomatic endocrinopathy event has been identified, otherwise PDR001 must be permanently discontinued.

Endocrine events (NCI-CTCAE v4.03)		
Grade	Recommended Adverse Event management guidelines	Mandatory Dose Modification requirements
		2 nd occurrence: Permanently discontinue PDR001
Autoimmune diabetes (Grade 3 or symptomatic hyperglycemia)	Initiate anti-glycemic therapy (i.e. insulin) as medically indicated and monitor glucose levels regularly until metabolic control is achieved	Interrupt treatment until glucose returns to Grade 1 or baseline and then restart PDR001
Autoimmune diabetes (Grade 4 hyperglycemia or life-threatening complications)	Same as Grade 3	Permanently discontinue PDR001

Table 6-9 Mandatory dose modification requirements and recommended clinical management guidelines for infusion reaction events and cytokine release syndrome

Infusion reaction (NCI-CTCAE v4.03)		
Grade	Recommended Adverse Event management guidelines	Mandatory Dose Modification requirements
Grade 1 Mild reaction; infusion interruption not indicated; intervention not indicated	Increase monitoring of vital signs as medically indicated until the patient is deemed medically stable in the opinion of the investigator.	Continue PRD001 treatment

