Grade 2 Requires infusion interruption but responds promptly to symptomatic treatment (e.g., antihistamines, NSAIDS, narcotics, IV fluids); prophylactic medications indicated for ≤24 hrs	
 ● Stop Infusion ● Additional appropriate medical therapy may include but is not limited to: 
 ● IV fluids ● Antihistamines ● NSAIDS ● Acetaminophen ● Narcotics ● Increase monitoring of vital signs as medically indicated until the patient is deemed medically stable in the opinion of the investigator. ● If symptoms resolve within one hour of stopping drug infusion, the infusion may be restarted at 50% of the original infusion rate (e.g. from 100 mL/hr to 50 mL/hr). Otherwise dosing will be held until symptoms resolve and the patient should be re-premedicated for the next scheduled dose. ● Patient may be premedicated 1.5hr (± 30 minutes) prior to infusion of PDR001 with: 
 ● Diphenhydramine 50 mg po (or equivalent dose of antihistamine). ● Acetaminophen 500-1000 mg po (or equivalent dose of analgesic). 	1 st occurrence: Continue PRD001 treatment at the same dose and schedule with premedication 2 nd occurrence: Despite premedication or prolongation of infusion, consider permanent discontinuation of PDR001.
Grade 3: Prolonged (i.e., not rapidly responsive to symptomatic medication and/or brief interruption of infusion); recurrence of symptoms following initial improvement;	
 ● Stop Infusion ● Additional appropriate medical therapy may include but is not limited to: 
 ● IV fluids ● Antihistamines ● NSAIDS ● Acetaminophen ● Narcotics 	Permanently discontinue PDR001

Infusion reaction (NCI-CTCAE v4.03)		
Grade	Recommended Adverse Event management guidelines	Mandatory Dose Modification requirements
hospitalization indicated for other clinical sequelae (e.g., renal impairment, pulmonary infiltrates) Grade 4: Life-threatening; pressor or ventilatory support indicated	
 • Oxygen • Pressors • Corticosteroids • Epinephrine 
 • Increase monitoring of vital signs as medically indicated until the patient is deemed medically stable in the opinion of the investigator. Hospitalization may be indicated.	

Table 6-10 Mandatory dose modification requirements and recommended clinical management guidelines for “other” potential immune-related AEs of special interest

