6.3.1.2.2 Guidance for corticosteroids tapering for management of immune-related AEs

Reduce prednisone dose by 2.5- to 5.0-mg decrements every 3–7 days until physiologic dose (5 to 7.5 mg of prednisone per day) is reached. Consider to complete tapering over a period of at least 4 weeks. Slower tapering of corticosteroids therapy may be recommended if the adverse event is not showing improvement. Once corticosteroid tapering is achieved at a level of 10 mg of prednisone/day (or equivalent), treatment with PDR001 can be restarted as indicated in the dose modification tables.

6.3.1.3 Dose modification requirements for adverse events suspected to be related to study treatment

The required dose modification and management of adverse events that are considered to be related to study medication and do not have specific management requirements noted elsewhere in the protocol are provided in [Table 6-11](#) and [Table 6-12](#).

Table 6-11 Mandatory dose modification requirements and recommended clinical management guidelines for hematologic adverse events suspected to study treatment

Hematologic suspected AEs (NCI-CTCAE v4.03)		
Grade	Recommended Adverse Event management guidelines	Mandatory Dose Modification requirements
Neutropenia		
Grades 1, 2	NA	Continue PDR001 treatment
Grade 3, 4	Monitoring blood test more frequently (every 7 days for grade 3, and 3-5 days for grade 4)	
1st occurrence:
 
 Interrupt PDR001 until toxicity recovers to Grade ≤2 or baseline. 
 Once recovered restart PDR001 treatment at the same dose and schedule 
2nd occurrence:
 
 Interrupt PDR001 until toxicity recovers to Grade ≤2 or baseline 
 Once recovered restart PDR001 treatment at the same dose and schedule 
AE resolution to ≤ Grade 2 or baseline must occur within a maximum period of 12 weeks since Grade 3 or 4 event has been identified, otherwise PDR001 must be permanently discontinued
 
3rd occurrence: Permanently discontinue PDR001.

Febrile Neutropenia	Apply Institutional guidelines	Follow- neutropenia Grade 4 requirements (above)
Thrombocytopenia (NCI-CTCAE v4.03)		
Grade 1, 2, 3 without clinical significant bleeding	Grade 3: monitoring blood test more frequently (every 7 days)	Continue PDR001 treatment

Hematologic suspected AEs (NCI-CTCAE v4.03)		

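### Section 6.1.2 contemplates resuming PDR001 after a severe anaphylactic reaction, while the mandatory Table 6-9 stops the drug permanently for grade 3 and 4 infusion reactions; the 6.1.2 sentence should be made subject to the table

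*Protocol*

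**What the plan says.** Section 6.1.2 (Ancillary treatments) requires the infusion to be stopped at once if a severe anaphylactic or anaphylactoid reaction occurs, and then adds: "The patient may only resume study treatment following discussion with Novartis". It gives no grade and no criteria for that discussion. The same section refers to Section 6.3.1.2 for the management of PDR001 infusion reactions. It also lets the investigator record such a reaction under another CTCAE category, anaphylaxis and allergic reaction among them, if that fits better.

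Table 6-9, in Section 6.3.1.2, is titled as "guidelines for infusion reaction events and cytokine release syndrome". For grade 3 and grade 4 its mandatory column says to discontinue PDR001 permanently, with no exception. Grade 4 is described as "Life-threatening; pressor or ventilatory support indicated", and the treatments listed for grades 3 and 4 include pressors and epinephrine. On the status of that column, Section 6.3.1.2.1 states: "The dosing modification requirements are mandatory".

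**The concern.** A severe anaphylactic reaction to the infusion falls within both instructions. A site that opens Section 6.1.2 learns that treatment may resume once the sponsor has been consulted. A site that opens Table 6-9 learns that the drug must be stopped for good. No sentence ranks one above the other.

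The stake is patient safety: re-exposing a patient whom the table bars from further dosing. The protocol is cautious elsewhere. Exclusion criterion 12 keeps out patients with severe hypersensitivity to other monoclonal antibodies where the investigator sees an increased risk of a serious infusion reaction. An open door after a severe reaction to PDR001 itself sits badly with that. The rule is still live, because Section 6.1.5 allows dosing to continue after the 10-Aug-2018 cut-off.

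**Working it through.** The conflict is a matter of reading, and the plan gives no figure to reproduce. The provisions compare as follows.

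| Provision | Event | Action on PDR001 | Sponsor discussion |
|---|---|---|---|
| Section 6.1.2 | Severe anaphylactic or anaphylactoid reaction, no grade given | Stop this infusion; later resumption contemplated | Required before resuming |
| Table 6-9, grade 2 | Infusion must be interrupted, prompt response to treatment | First occurrence: continue with premedication. Second: consider permanent discontinuation | Not mentioned |
| Table 6-9, grades 3 and 4 | Prolonged or recurrent symptoms, hospitalization, or life-threatening reaction | Permanent discontinuation | Not mentioned, no exception |

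1. **Do they cover the same event?** Table 6-9 defines its rows by clinical features, not by the recorded term. A reaction needing epinephrine, pressors or ventilatory support is within its grade 3 and 4 rows in substance.

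2. **What grade is severe?** Section 6.1.2 does not say. Table 6-10 equates severe with grade 3. Section 8.1.1 uses the same mapping where CTCAE has no grading. Taking severe as grade 3 or higher is therefore a supported inference, but still an inference.

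3. **Do they conflict?** On that inference, yes: one text contemplates resumption and the other rules it out.

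4. **Which should govern?** Three things favour Table 6-9. Its dose column is mandatory. Section 6.1.2 treats anaphylaxis as a possible label for a PDR001 infusion reaction and sends infusion reactions to Section 6.3.1.2. Section 12 forbids asking the sponsor to approve deviations, so a discussion under 6.1.2 could not waive the table. None of these states that the 6.1.2 sentence yields.

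**How often could it matter?** Section 1.2.1.2 lists the grade 3/4 events suspected to be related to treatment among 160 patients in the first-in-human study. No infusion reaction or anaphylaxis is in the list. With 0 events in n patients, the exact two-sided 95% upper limit is 1 − 0.025^(1/n):

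- n = 160: 1 − 0.025^(1/160) = 0.0228, or 2.3%.
- At that limiting rate, the expected number among the 116 patients enrolled would be 116 × 0.0228 = 2.6.

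The second figure is an expectation at the upper confidence limit, not a maximum count. It also overstates current exposure, because enrolment is closed and only patients still on treatment can be affected; their number is not given. Doses in the 160-patient study were mixed. This trial's own interim summary lists no infusion reaction or anaphylaxis either, but for grade 3/4 it reports only events seen in at least two patients per group, so a single case is not excluded.

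**The case against.** The strongest reply is that the 6.1.2 sentence restricts and does not permit. It states a necessary condition for resuming. The patient must also satisfy the mandatory table, and Section 12 rules out a sponsor waiver. Read cumulatively, 6.1.2 adds a check and Table 6-9 sets the stop, so there is no strict logical contradiction. The infusion is stopped at once, and resuscitation equipment and a physician must be at hand.

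Much of this stands, and it is why the better reading is that re-exposure is already barred. But on the cumulative reading the sentence has no grade 3 or 4 case left to apply to. It would matter only for a reaction judged severe yet graded 2, and it does not say so. A site is more likely to take it as a route back to treatment. The bedside safeguards reduce harm but do not settle which rule applies.

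A reader might go further and infer that the recorded CTCAE term decides the outcome: an event coded as anaphylaxis would escape Table 6-9, reach Table 6-12, and so be open to restart after a first and a second grade 3 event. In support, the Table 6-9 title does not name anaphylaxis, Section 7.2.7 lists it beside infusion-related reaction, and Section 6.3.1.2.1 has a fallback for unlisted events: "In cases where the specific irAEs are not listed in the tables below, the investigator should follow the dose modification requirements in" Section 6.3.1.3. The documents do not support that reading:

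- Section 6.3.1.3 covers only related events that "do not have specific management requirements noted elsewhere in the protocol". Severe anaphylactic reactions have such requirements in 6.1.2 itself and, in substance, in Table 6-9.
- The coding sentence in 6.1.2 is about how to describe PDR001 infusion reactions, so the alternative label does not take the event out of that class.
- Section 7.2.7 governs when to draw an extra blood sample, not dosing.
- Grade 4 is closed separately for immune-related events: "Any grade 4 irAE must result in permanent discontinuation of PDR001".

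**Conclusion.** The point holds as an unresolved conflict between two instructions in the protocol, and it should be corrected. Section 6.1.2 contemplates resumption after sponsor discussion; Table 6-9 requires a permanent stop at grades 3 and 4; no text ranks them. Table 6-9 is the better authority, so the error lies in the 6.1.2 sentence. It does not follow that the protocol as a whole permits re-exposure.

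The conclusion rests on taking severe as grade 3 or higher. The likely number of patients is small, for the reasons given with the calculation. The ORR analysis, the success criteria and the sample size are untouched. What justifies acting is the seriousness of the possible harm against a very cheap correction.

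**What to change.** Keep the sponsor discussion in Section 6.1.2, but make it subject to Table 6-9. Suggested wording: *Anaphylactic, anaphylactoid or allergic reactions to the PDR001 infusion are handled by grade under Table 6-9, whichever CTCAE term is recorded; at grade 3 or higher PDR001 is permanently discontinued. After a lower-grade reaction that the investigator judges severe, dosing may restart only if Table 6-9 allows it and the case has first been discussed with the sponsor.*

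The second sentence is needed. Deleting the discussion outright would leave a reaction judged severe but graded 2 under Table 6-9 alone. There the infusion may restart at half the original rate if symptoms clear within an hour, with no sponsor contact.

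The cost is one wording change by written amendment, with the approvals that Section 12.1 requires. The clinical downside is no rechallenge after a grade 3 reaction, which Table 6-9 already forbids. Nothing changes in data collection or the SAP.
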